### 3.5 CASE RECORD FORMS AND QUESTIONNAIRES

#### 20. LIST OF QUESTIONNAIRES

Table 1. List of outcome measures

Outcome measure	Baseline	3	6	12
Demographic Factors: Age, sex, ethnicity, employment, education, marital status	✓			
Event type - stroke and pathological subtypes, or TIA and event date (physician diagnosed)	✓			
Hospitalization details: hospital, date of admission, date of discharge	✓			
Event details (revascularization and planned procedures) from medical records	✓			
Hospital Anxiety and Depression Scale	✓	✓	✓	✓
Stroke awareness (recognition of risk factors, knowledge of actions) [61]	✓	✓	✓	✓
Quality of life (EQ-5D-5L) [62]	✓		✓	
Cognitive functioning by MoCA [63]	✓		✓	
Medication adherence and self-efficacy (SEAMS) REF)	✓	✓	✓	✓
Physical measurements (non-fasting blood test, SBP/DBP, BMI, HR)*	✓		✓	
Absolute and relative 5-year risk of stroke (as measured by Stroke Riskometer app)	✓		✓	
Lifestyle factors (Diet score, physical activity, smoking, alcohol)	✓	✓	✓	✓
CVD outcomes, recurrent events, hospitalisation (stroke, CVD events) self-report and/or from clinical records	✓	✓	✓	✓
Health and Service costs: NMDS (NZ)			✓	✓
Productivity level NMDS (NZ)	✓	✓	✓	✓
Participant feedback questionnaire – Intervention group only	✓	✓	✓	✓

Items will include demographic factors, medical history, lifestyle risk factors, awareness of stroke risk factors, warning signs, symptoms and actions;[64] depression screening test (Hospital Anxiety and Depression Scale) health related quality of life ([EQ-5D-5L](#)),[62] health-care resource

use questionnaire, cognitive assessment (Montreal Cognitive Assessment MoCA) and participant satisfaction questionnaires. See 2 for details of measures collected at each timepoint. Life's Simple 7 score will be calculated from corresponding measurements of smoking, BMI, physical activity, healthy diet score, blood total cholesterol, glucose level and BP.[37]

Table 2. Life's Simple 7

Modifiable factors	Poor health	Intermediate health	Ideal health
Smoking status	Current smoker	Former ≤ 12 months	Never or quit > 12 months
Body mass index	≥ 30 kg/m 	25–29.9 kg/m 	< 25 kg/m 
Physical activity	No physical activity	1–3 times, less than 2.5 hours per week	≥ 4 times per week, 2.5 hours or more
Healthy diet score	0–1 component	2–3 components	4–5 components
Total cholesterol	≥ 240 mg/dL	200–239 mg/dL or treated to goal	< 200 mg/dL

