## 31. SECONDARY END POINTS

Secondary outcomes include: (1) difference in the mean change in the LS7 scale score at 6 months post-randomisation between UC and HWC (2) the change in individual lifestyle components of the LS7 scale (BMI, smoking, physical activity, and diet) at 6 and 12 months; (3) diastolic BP (mmHg); (4) quality of life (EQ-5D-5L), (5) awareness of stroke risk factors and warning signs, (6) medication adherence (7) cognitive outcomes (8) adverse events including hospitalisations; and (9) health service use and costs.

The LS7 scale includes BP, cholesterol, blood glucose, BMI, smoking, physical activity, and diet. The score of LS7 will be calculated by providing 2 points for ideal, 1 point for intermediate, and 0

points for poor status of each of the 7 individual factors. Ideal levels of health factors were: non-smoker or quit >1 year ago; BMI <25 kg/m^2; BP <120/80 mm Hg; total cholesterol <200 mg/dL; fasting blood glucose <100 mg/dL; ≥150 min/week of physical activity; and a healthy diet score (≥4 components). Study participants who were treated to target levels for hypercholesterolemia, hypertension, or diabetes mellitus were classified as intermediate for the respective health factor. Thus, the LS7 summary score will range from 0 to a maximum of 14 points, with a higher score indicating healthier status.

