### Part I: Physical activity

15I.1. How often do you perform moderate to vigorous physical activity for at least 10 minutes that makes you breathe harder/break into a sweat?

- 4 times a week or more  
 1-3 times a week  
 Never

15I.1.1. How many hours per week would you spend performing these physical activities?

- Less than 2.5 hours per week  
 2.5 hours per week or more

15I.2. LS7 Activity score

\_\_\_\_\_

15J. Total LS7

\_\_\_\_\_

Note: Score out of 14.

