### Part I: Physical activity

15I.1. How often do you perform moderate to vigorous physical activity for at least 10 minutes that makes you breathe harder/break into a sweat?

4 times a week or more  
 1-3 times a week  
 Never

15I.1.1. How many hours per week would you spend performing these physical activities?

Less than 2.5 hours per week  
 2.5 hours per week or more

15I.2. LS7 Activity score

\_\_\_\_\_

15J. Total LS7

\_\_\_\_\_

Note: Score out of 14.

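### Table 2's physical-activity row covers only two of the four active answer combinations on the forms and conflicts with the protocol's 150 min/week definition of ideal; no governing rule is named

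*Protocol*

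**What the plan says.** The protocol describes the LS7 physical-activity score in several places.

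- **Section 20, Table 2.** Poor is "No physical activity", intermediate is "1–3 times, less than 2.5 hours per week", and ideal is "≥ 4 times per week, 2.5 hours or more". Frequency and duration are joined by a comma.
- **Section 4 and section 31.** Both define ideal by weekly time, with no frequency condition; section 31 has "≥150 min/week of physical activity". Section 31 also assigns 2, 1 and 0 points to ideal, intermediate and poor.
- **Assessment information, Table 3.** The bands are zero, above zero but under 150, and 150 or more minutes of moderate or mixed activity, with a 75-minute alternative for vigorous activity. There is no frequency condition. The row is labelled per day, not per week.
- **Appendix C, Forms B and F, Section 15 Part I.** One item asks "How often do you perform moderate to vigorous physical activity for at least 10 minutes that makes you breathe harder/break into a sweat", with three answers ("4 times a week or more", 1–3 times, or never). A separate item asks "How many hours per week would you spend performing these physical activities", with two answers split at 2.5 hours. The score field, "15I.2. LS7 Activity score", is blank and carries no printed rule.

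Section 31 makes the LS7 total at 6 months a secondary endpoint. It does the same for the lifestyle components, including physical activity, at 6 and 12 months.

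**The concern.** The form answers use exactly the cut-points of Table 2, so a data manager would naturally take Table 2 as the scoring rule. Applied as printed, it has no row for some ordinary answers, and for one of them it disagrees with section 31.

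Whoever programs the score must then choose between leaving the domain missing, picking a point value, or using another definition in the protocol. A missing domain would also leave the 14-point total undefined. A 1-point difference can move a participant across an LS7 category boundary (4 to 5, or 9 to 10). That matters because section 11 also lists movement between LS7 risk levels as a secondary outcome. If the choice is made after data are in hand, it becomes an avoidable post hoc decision on secondary endpoints.

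**Working it through.** No figure in the plan needs reproducing. The check is an enumeration of the form answers against each rule.

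**Inputs.** Frequency (item 15I.1): never, 1–3, or 4 or more times a week. Hours (item 15I.1.1): under 2.5, or 2.5 or more. Points: 2, 1, 0 (section 31). Conversion: 2.5 h × 60 = 150 min, so the form's hours cut-point is the 150-minute threshold of sections 4 and 31.

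**Rules compared.**
- A: Table 2, both conditions required in each row.
- B: Table 2, the comma read as *or* in the intermediate row only.
- C: Table 2, the comma read as *or* in both rows.
- D: weekly time only. Ideal is taken from sections 4 and 31; the intermediate band is taken from Table 3, read per week.

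| Frequency | Hours | A | B | C | D |
|---|---|---|---|---|---|
| Never | – | 0 | 0 | 0 | 0 |
| 1–3 | under 2.5 | 1 | 1 | 1 | 1 |
| 1–3 | 2.5 or more | none | 1 | 1 and 2 | 2 |
| 4 or more | under 2.5 | none | 1 | 1 and 2 | 1 |
| 4 or more | 2.5 or more | 2 | 2 | 2 | 2 |

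**Results.**
- Under A, 2 of the 4 active combinations have no category.
- Under B every answer has a score, but 1–3 times with 2.5 hours or more gets 1, against 2 under D. The difference is 2 − 1 = 1 point.
- Under C both combinations fall in two categories at once.
- Under D all four active combinations have exactly one score.

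**Both gaps are ordinary patterns.** Three 60-minute sessions give 3 × 60 = 180 min, which is ideal by time but has no row under A. Five 20-minute sessions give 5 × 20 = 100 min, which is intermediate by time but also has no row under A.

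**The two gaps differ in kind.** The combination of 1–3 times with 2.5 hours or more contradicts sections 4 and 31. The combination of 4 or more times with under 2.5 hours is only an omission: Table 3's band scores it 1, and neither section 4 nor section 31 gives it a competing value.

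**Size.** The discrepancy is at most 1 point of 7 × 2 = 14 per affected participant. The protocol gives no distribution of activity answers, so the number affected cannot be computed.

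**The case against.** The strongest reply is that Table 2 is simply the outlier. Sections 4 and 31 and Table 3 all work by time, and together they give every form answer a score once Table 3's unit label is set aside. Because 2.5 hours is exactly 150 minutes, one can also read hours as the operative criterion in Table 2 and frequency as description. Table 2 is then complete and agrees with the rest. The mapping of answers to scores could be settled in an analysis plan or data dictionary, and nothing already collected is lost.

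Much of this stands. It shows that a workable rule is already in the protocol and that the repair is small. It does not remove the inconsistency. Nothing in the text says that frequency is only descriptive, and nothing says which definition governs. The blood pressure row of the same table writes out *and* and *or*; the activity row does not. These are rules the protocol has chosen to state and that disagree, which is different from a detail properly left for later.

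Three stronger inferences are tempting but unsupported.

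- *The forms leave participants unscored.* The forms print no scoring rule for this item, and the REDCap calculation is not shown. Missing scores follow only if Table 2 is applied with both conditions.
- *A 1-point error swamps the effect.* A reader might set it against the coached arm's LS7 change in the previous trial (section 6: 7.39 − 7.08 = 0.31). That is an arm mean, whereas 1 point is an individual difference. With one rule in both arms, the choice between B and D alters the between-arm contrast only by the arms' difference in change in the share giving 1–3 times with 2.5 hours or more. As an assumption only, a difference of 5 to 10 percentage points would give 0.05 to 0.10 points.
- *Coaching pushes people into these combinations.* The protocol contains nothing to show it.

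**Conclusion.** The point holds as an inconsistency between stated scoring rules. With both conditions required, Table 2 leaves two of four active answer combinations without a category. One of these contradicts the time-only definition of ideal in sections 4 and 31; the other is an omission. The activity component and the LS7 total can differ by up to 1 point for an affected participant, depending on which rule is used.

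The conclusion rests on reading Table 2's comma as requiring both conditions. Reading it as *or* in the intermediate row still conflicts with section 31, and reading it as *or* in both rows is ambiguous. Only treating frequency as irrelevant resolves the conflict, and the protocol does not say to do that. The proportion affected, and hence any effect on the LS7 comparison, cannot be stated from the document. The primary endpoint, systolic blood pressure, is unaffected. This is a modest but worthwhile correction to secondary endpoints.

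**What to change.** State one rule for item 15I.2, based on weekly time: 0 for never, 1 for any activity but under 2.5 hours a week, 2 for 2.5 hours a week or more. Then:

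- remove the frequency condition from Table 2;
- change the Table 3 row to minutes per week, and drop or reconcile its 75-minute vigorous criterion, which the forms cannot apply because they do not separate moderate from vigorous activity;
- print the rule beside item 15I.2 on Forms B and F;
- program the REDCap score to match, before any scoring is done.

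The cost is two table edits, a line on each form and one formula. The answers already asked for contain everything needed, so no new data collection is required.

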## ASSESSMENT INFORMATION

The Primary Outcome measure of **blood pressure** will be collected as part of the LS7 questionnaire. The LS7 is a simple scoring system to assess cardiovascular health with scores ranging from 0 to 14, with the overall LS7 score categorised as inadequate (0–4), average (5–9), or optimum (10–14) cardiovascular health. These are; blood pressure, cholesterol, glucose, body mass index, smoking, physical activity, and diet.[37] The total LS7 score as well as individual LS7 items apart from blood pressure are secondary outcomes.

## The Life's Simple 7 scale

Table 3. Definitions of the LS7 categories \*

Life's Simple 7	Level of Cardiovascular Health		
	Poor	Intermediate	Ideal
Lifestyle Factors			
Body mass index, kg/m 	≥30	25.0–29.9	<25
Physical activity, min/day	0 MVPA	>0 – <150 MPA or MVPA >0 to <75 VPA	≥150 MPA or MVPA ≥75 VPA
Healthy diet score	0–1 components	2–3 components	4–5 components
Cigarette smoking	Current	Quit <12 months ago	Never or quit >12 mo
Medical risk factors			
Blood pressure, mmHg	≥140/≥80	120 – 139/80–89 or <120/<90 with med	<120/<80 no med
Total cholesterol, mg/dL	≥240	200–239 or <200 with medication	<200
Fasting blood glucose, mg/dL	≥126	100–125	<100
Glycosylated Hemoglobin, %	≥6.5 or taking diabetes med	5.7–6.4	<5.7

M, moderate; V, vigorous; PA, physical activity.

(i) Fruits and vegetables ≥4.5 cups/day; (ii) Fish 3.5-oz servings (preferably oily fish) ≥2 servings/week; (iii) Sodium <1500 mg/day; (iv) Sweets/sugar-sweetened beverages ≤450 kcal (36 oz)/week; (v) Whole grains (1.1 g of fiber in 10 g of carbohydrates), 1-oz-equivalent servings ≥3 servings/day.

\*Note: Fasting blood glucose in mmol/l is ≥7.00 (poor), 5.55–6.99 (adequate) and <5.55 (optimum). Plasma total cholesterol, mmol/l ≥ 6.22 (poor), 5.18–6.21 (adequate) < 5.18 (optimum).

## Hospital Anxiety and Depression Scale (HADS)

The HADS is a commonly used scale to identify anxiety and depression disorders, including stroke and TIA patients [65-67]. The scale has seven items for depression and seven items for anxiety, with a total possible score of 0-21 for each, with 0-7 being = normal, 8-10 – borderline abnormal, and 11-21 = abnormal. As part of the screening for TIIPS, those who score ≥11 on either the depression or anxiety items will not be eligible to participate in the trial.

## Stroke Awareness questionnaire

Stroke awareness is an essential aspect of stroke prevention. Being aware of stroke risk factors allows individuals to make lifestyle changes. Being aware of stroke signs and symptoms allows individuals to recognise the signs if they or someone they know experience stroke and action a call to emergency services/healthcare. The stroke awareness questionnaire is adapted from an Australian telephone community survey [68] to determine baseline knowledge regarding stroke risk factors, symptoms, treatment, and information resources.[64]

## **Montreal Cognitive Assessment**

The Montreal Cognitive Assessment (MoCA) [63] was designed as a rapid screening instrument for mild cognitive dysfunction. It assesses different cognitive domains: attention and concentration, executive functions, memory, language, visuoconstructional skills, conceptual thinking, calculations, and orientation. Time to administer the MoCA is approximately 10 minutes. The total possible score is 30 points; a score of 26 or above is considered normal.

## **Modified Rankin Scale (mRS).**

The modified Rankin Scale (mRS) is commonly used in the stroke setting as a scale for assessing the level of disability or dependence in daily activities.[69] It is widely used in stroke clinical trials to assess improvements in disability levels. The scale ranges from 0 to 6, with 0 denoting no symptoms at all, to 6 for death. The Figure below shows the individual items of the mRS. In this study, those participants with an mRS score of 0-2, denoting independence in all personal activities without assistance, will be eligible for the trial.

## **Self-Efficacy For Appropriate Medication Use Scale (SEAMS)**

SEAMS is a self-efficacy scale for medication adherence in chronic disease management that can be used in patients with a broad range of literacy skills.[70] It is a reliable and valid instrument for assessing medication self-efficacy in chronic disease management. Participants are asked to choose their level of confidence in taking medications correctly under different circumstances (1 = not confident, 2 = somewhat confident, and 3 = very confident). It was designed for patients with low literacy. The total score ranges from 13 to 39 where low scores indicate a low level of confidence and high scores indicate a high level of confidence. The SEAMS questionnaire has been used in a range of chronic condition settings such as secondary prevention of cardiovascular diseases. [71-73]

## **Participant Satisfaction with Life**

The Cantril's ladder[74] is a self-reported subjective measure of Satisfaction with life two item scale is a simple ladder scale asks respondents to think of a ladder, with their best possible life being a 10, and the worst possible life being a 0. They are then asked to rate their own current lives on that 0 to 10 scale. Participants are also asked to imagine their life in the best possible light and to describe their hopes and wishes for the future. Scoring: Low <6 points, Medium 6–7 points, and

High 8 points. This is used in several studies including older populations as a measure of life satisfaction. [75, 76]

The Satisfaction with Life Scale [77] [78] is a five item scale to measure general life satisfaction and subjective well-being, and is used in chronic conditions such as Parkinson's disease. [79]

### **Stroke Riskometer stroke risk assessment**

The validated Stroke Riskometer is a mobile application that is free to download from App stores. The Stroke Riskometer App [80] is a novel, evidence-based app for the primary prevention of stroke. The App incorporates several evidence-based tools to promote behaviour change aligned with internationally recognised stroke prevention guidelines.[81] These include:

- Provision of feedback on *absolute* risk of stroke within the next 5 to 10 years *and* compares a person's *relative* risk with those of a person of the same age and sex without risk. This approach has been demonstrated to motivate behaviour change when used in conjunction with other methods.[82]
- Employs *tailored self-management* strategies including goal setting to engage the person in behaviour modification
- Includes *information on stroke risk factors and warning signs* aligned with the internationally relevant Face, Arm, Speech, Time (FAST) international mass media campaign.
- Uses *reminders*, known as “push notifications”, to prompt users to achieve their goals. Such reminders have been shown to increase adherence to programs.[83]

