# TRIAL OF AN INDIVIDUALISED INTERVENTION FOR THE PREVENTION OF STROKE (TIIPS)

## BACKGROUND AND RATIONALE

### 1. THE IMPACT OF TIA/MINOR STROKE

Patients with Transient Ischaemic Attack (TIA) and minor (non-disabling; (NIHSS  $\leq$  3)[1] stroke are at high risk of secondary vascular events, including major stroke, myocardial infarction (MI), cognitive deficits and death, with population-based studies reporting incidence of adverse outcomes as high as 25% within 90 days.[2] New vascular events, including fatal strokes, MI, and other cardiovascular deaths, occur in up to 26% of patients within four years post-TIA.[3, 4] Increased risk is associated with an unhealthy lifestyle and poor adherence to medications to treat elevated blood pressure, diabetes mellitus, and previous vascular disease.[3] ARCOS-IV[5] showed that the age-standardised incidence of first-ever TIA in NZ is one of the highest among developed countries at 50 [95%CI 46-55] per 100,000 persons in 2011-2012.[6] TIA occurred at a younger mean age in Māori and Pacific people (60 years) and Asian and other (including Middle Eastern and African) people (68 years) compared to Europeans (74 years).[6] ARCOS-IV also found a high prevalence of cardiometabolic risk factors (e.g. 65% had hypertension, 47% had elevated lipids, and 27% had atrial fibrillation).

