### 11. SECONDARY AIMS

The **secondary aims** are to determine the effectiveness of HWC in improving

1. Overall cardiovascular disease (including stroke) risk at 6 months post-randomisation based on the LS7 compared to Baseline

2. Individual LS7 behavioural risk factors at 3-, 6- 9- and 12- months post-randomisation compared to Baseline
3. Awareness about stroke symptoms, risk factors and their management 6- and 12- months post-randomisation compared to Baseline
4. Quality of life, at 6- and 12- months post-randomisation compared to Baseline
5. Cognitive outcomes at 6-, and 12- months post-randomisation compared to Baseline
6. Mood outcomes compared to Baseline
7. Adherence to CVD medications at 3, 6-, and 9 and 12- months compared to Baseline
8. CVD/adverse outcomes at 12 months post randomisation.
9. Health and service costs at 12 months post randomisation
10. Productivity status at 12 months post randomisation

Secondary outcomes are:

1. systolic blood pressure, total cholesterol, blood glucose at 6-months post randomisation
2. change in proportion of participants in 'high' and 'intermediate' to 'low' risk on LS7 at 6-months post randomisation
3. Stroke risk from Stroke Riskometer – 5- year absolute and relative risk at 6- and 12-months post randomisation
4. Quality of life (EQ5D) at 6-months post randomisation
5. Stroke awareness at 6- and 12-months post randomisation
6. Cognitive assessment score (Montreal Cognitive Assessment)
7. Medication adherence (Self-Efficacy For Appropriate Medication Use Scale (SEAMS))
8. CVD adverse outcomes (fatal and nonfatal stroke, TIA, myocardial infarction and heart failure, death attributable to CVD and all-cause mortality)
9. Healthcare and community service costs assessed as self-reported service use questionnaire at follow up. Productivity status will be self-reported and will include items regarding status (e.g., paid work, voluntary work, homemaker, student, unemployed), hours (e.g., full/part time), compared to hospitalisation pre-stroke status.

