## PARTICIPANT RECRUITMENT

### 12. INCLUSION CRITERIA

1. People aged between 18 years to 75 years diagnosed with TIA or first-ever minor stroke (excluding subarachnoid haemorrhage (SAH)) (National Institutes of Health Stroke Scale (NIHSS) score  $\leq$  4) and/or modified Rankin Scale (mRS) score 0-2 at discharge [1] in the past 6 weeks

2. Admitted to one of the three Auckland based hospitals or identified via primary care for minor stroke or TIA
3. Who can converse in English
4. Provides written informed consent
5. Exclusion criteria
6. History of major stroke or myocardial infarction (verified through Clinical Portal medical records)
7. Planned carotid endarterectomy
8. Life-threatening conditions with a life-expectancy <5 years
9. Current (in the past year) significant clinical depression/anxiety (Hospital Anxiety and Depression questionnaire (HADS)  $\leq 11$  in either or both the depression and anxiety domains) (either in clinical records or at screening) OR psychiatric conditions (based on medical records),
10. History (past year) of alcohol or drug/substance abuse
11. Dependent on others (living in a rest-home/care facility)
12. Significant cognitive impairment or pre-existing diagnosis of dementia e.g. ACE-R  $\leq 82$  (from clinical records), or at screening (MoCA (<26))
13. Participation in another RCT

The majority of the inclusion and exclusion criteria will be determined by means of medical record/clinical portal screening, completed by hospital based research staff. If all the relevant information is not available, the initial section of the Baseline assessment will allow further screening to check for remaining criteria (e.g. cognitive impairment or abnormal mood). Exclusion due to significant anxiety and depression [58, 59] or cognitive impairment [60] are necessary in order to recruit participants who will be able to engage effectively with the study over a period of 12 months.

---

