## HEALTH ECONOMIC EVALUATION

The net costs and benefits of the intervention compared to the control will be described and reported in accordance with the Consolidated Health Economic Evaluation Reporting Guidelines (CHEERS). [97] For each intervention arm, the probability of resource use and associated costs will be reported. Cost estimates will be presented in terms of direct costs (e.g., healthcare), indirect costs (e.g. lost productivity) and out-of-pocket costs. Unit prices for resources utilised will be sourced from the most appropriate and up-to-date source (e.g., PHARMAC). Costs will be measured in actual prices for the reference year (e.g., 2023). Where prices in 2023 are unavailable, adjustment to the actual price will be made using the published health sector specific deflator/inflators. The overall 'Program Costs' (i.e., non-research related costs associated with providing the intervention) will be deducted from the potential cost-offsets from fewer readmissions or other resource savings. Sensitivity and uncertainty (probabilistic multivariable [Monte-Carlo simulated]) analyses to account for variability in point estimates will be performed to assess the robustness of results.

The analysis will include modelling the potential opportunity cost savings from future strokes averted based on changes in risk profile (e.g., change in absolute 5-year risk of stroke or clinically relevant change in LS7 score). An incremental cost/ quality-adjusted life year (QALY) gained will also be calculated. The EQ5D is the most commonly used in economic evaluations to estimate preference-based outcome measure and will be used to calculate QALYs for the cost utility analysis.[62, 98] Threshold and willingness-to-pay analyses, illustrated using cost effectiveness acceptability curves, will be performed to assess uncertainty in the model parameters or a range of different scenarios, to explore under what conditions HWC could be cost effective and yield potential cost offsets/savings. Potential savings will be calculated using a "case-averted" approach, which estimates the direct and indirect costs savings if the use of HWC leads to annual reduction in stroke incidence. These estimates will be extrapolated to the overall New Zealand population.

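### The protocol presents the Stroke Riskometer only as a primary-prevention tool and gives no support for reading its score as absolute 5-year stroke risk after a recent TIA or minor stroke

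*Protocol*

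**What the plan says.** - **Instrument.** Under Assessment Information, the Stroke Riskometer section says: "The Stroke Riskometer App [80] is a novel, evidence-based app for the primary prevention of stroke". It calls the app validated but names no validation population. The app gives an absolute risk over 5 to 10 years and also "compares a person's *relative* risk with those of a person of the same age and sex without risk".
- **Population.** Section 12 admits people "diagnosed with TIA or first-ever minor stroke" in the past 6 weeks.
- **Outcome.** Secondary outcome 3 in section 11 is the Riskometer's "5- year absolute and relative risk at 6- and 12-months post randomisation". Table 1 in section 20 lists it as "Absolute and relative 5-year risk of stroke (as measured by Stroke Riskometer app").
- **Power.** Section 32 claims 90% power for a 20% relative reduction in 5-year absolute stroke risk. It relies on New Zealand general-population data (n=1265, 0.07% incident stroke or TIA). The reference given, number 94, is the same Riskometer validation paper as reference 80.
- **Economics.** The Health Economic Evaluation section plans "modelling the potential opportunity cost savings from future strokes averted based on changes in risk profile (e.g., change in absolute 5-year risk of stroke"), and offers a clinically relevant LS7 change as the other example. Case-averted savings are then extrapolated to the New Zealand population.

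**The concern.** An absolute risk is only as good as its match to the people it is applied to. The protocol describes the app as a primary-prevention tool. Section 6 shows what the sponsor means by primary: its earlier primary-prevention trial left out people with a previous stroke or TIA. On that usage, the whole TIIPS sample lies outside the group for which the app is described.

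Two things are at stake. A secondary outcome could be reported as participants' 5-year stroke risk without any stated basis. If the same absolute change feeds the strokes-averted model, its scale passes into a cost saving that is projected to the national level.

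**Working it through.** **1. Support given for each instrument.** The HADS section refers to use in stroke and TIA patients. The SEAMS section refers to use in secondary prevention of cardiovascular disease. The Riskometer section refers only to primary prevention, and the guideline it cites for alignment (reference 81) is titled as one for primary prevention. The protocol does not list the algorithm's predictors, say whether a prior event is among them, or mention recalibration. So the support is absent, but invalidity is not shown.

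**2. The one related figure, 90% power (section 32).** Inputs are 180 per arm (Randomisation section), or 144 after 20% loss (180 × 0.80), two-sided 5%, and a 20% relative reduction.

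- *As an event comparison.* Power = Φ{[|p1 − p2| − 1.96√(2p̄(1 − p̄)/n)] / √([p1(1 − p1) + p2(1 − p2)]/n)}. With p1 = 0.0007 and p2 = 0.8 × 0.0007 = 0.00056, power is 2.8% at n = 180 and 2.8% at n = 144. The printed rate is also odd as a plain count, since 1265 × 0.0007 = 0.89 of a person.
- *As a score comparison.* The difference is 0.2 × mean, and the SD is CV × mean. For 90% power, CV ≤ 0.2 / [(1.960 + 1.282)√(2/n)]. This gives 0.585 at n = 180 and 0.52 at n = 144. The protocol states no SD or CV, so the 90% cannot be checked on this reading.

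The stated figure is therefore not reproduced from the rate beside it. This says nothing about the app's validity. It shows only that the 5-year-risk statement rests on general-population data.

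**3. Effect on strokes averted.** Let r0 and r1 be the mean Riskometer risks under usual care and coaching, b the true 5-year stroke risk under usual care in this population, and N the number of people.

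- Using the Riskometer's absolute difference: N(r0 − r1) = N·r0·(1 − r1/r0).
- Using a post-event baseline with the same relative change: N·b·(1 − r1/r0).
- The ratio of the first to the second is r0/b.

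The number of people and the relative change cancel, so everything depends on r0/b. The protocol gives no r0. It gives no b either. The nearest figure is in section 1, where new vascular events "occur in up to 26% of patients within four years post-TIA". That is an upper figure over four years. It covers all new vascular events, including myocardial infarction and cardiovascular death, so it cannot stand in for a 5-year stroke risk. The ratio could be below, at or above 1.

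**The case against.** **The protocol never says the score fails after an event.** Primary prevention describes the app's purpose. The algorithm may account for a previous stroke or TIA, and the cited validation paper is not part of the document. This stands. A reader might infer that the app measures a different quantity, or is uncalibrated in these participants. The document supports neither. What remains is that the sponsor cites nothing for this use.

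**The economic input is only an example.** The wording is "change in absolute 5-year risk of stroke or clinically relevant change in LS7 score", the Riskometer is not named there, and the model's baseline risk may be set in an analysis plan not shown here. Probabilistic, threshold and scenario analyses are planned. Most of this stands, so it would be too strong to say the model will use the Riskometer difference. Still, the Riskometer is the only 5-year-risk instrument in the protocol. The planned analyses would cover the issue only if the baseline risk is among the inputs varied, which the protocol does not say.

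**The authors are aware of post-event risk.** Section 32 discusses 5-year stroke risk after TIA and minor stroke and cites reference 4. This is true and helpful, because a suitable source is already cited. But section 32 does not link that risk to how the score is read.

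**The consequence is limited.** This is one of nine numbered secondary outcomes, relative risk is reported alongside absolute risk, and the same tool is used in both randomised arms. This stands in full.

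**Conclusion.** This is a cheap improvement, not a threat to the trial. The protocol describes the Riskometer only for primary prevention, applies it to people who have all had a recent TIA or minor stroke, and gives no basis for reading its output as their absolute 5-year stroke risk or for using its absolute change as an input for strokes averted.

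No size or direction of error can be stated. A reader might set the general-population rate or an assumed first-stroke risk against the 26% in section 1 and infer a large understatement of strokes averted. Any such factor would only be a ratio of chosen baseline risks, because the document contains neither quantity in r0/b.

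The systolic blood pressure outcome is unaffected. The between-arm difference in the score remains a fair comparison of risk-factor profile. The economic part of the point assumes that the 5-year risk named there is the Riskometer's.

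**What to change.** - **Secondary outcome 3 (section 11) and Table 1.** Report the Riskometer as a risk-factor score: the between-arm difference or ratio at 6 months, adjusted for baseline. Do not interpret it as absolute 5-year stroke risk unless validity after TIA or minor stroke is cited. If the algorithm handles a prior event, say so and give the source. In the same edit, reconcile the timing: section 11 lists 6 and 12 months, while Table 1 schedules only baseline and 6 months.
- **Health Economic Evaluation.** Take the baseline stroke risk from a post-TIA/minor-stroke source, for example the five-year cohort cited as reference 4. Apply the relative change to it instead of the Riskometer absolute difference. State the assumption that the relative change carries over to recurrent stroke. Vary the baseline risk in the sensitivity analysis, since section 32 suggests the New Zealand risk is higher than the European one.

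The cost is some wording and one changed model input, with no new data. The downside is a more modest claim for one secondary outcome.
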